4.1.3. Follow-up Period

Part 1 and Prevention Cohort of Part 2

Post-evaluation follow-up assessments will be conducted at Days 85, 141, and 169 according to the SoA. Strategies to manage infection risks and reduce the burden of return visits may be used by sites, such as remote visits.

Part 2 Treatment Cohort and Part 3

A post-evaluation follow-up assessment will be conducted at Day 85 according to the SoA. Strategies to manage infection risks and reduce the burden of return visits may be used by sites, such as remote visits.

4.2. Scientific Rationale for Study Design

This study is designed to evaluate the efficacy of a single dose of LY3819253, alone and in combination with LY3832479, compared to placebo in preventing and treating SARS-CoV-2 infection and COVID-19 in residents and facility staff at skilled nursing and assisted living facilities.

The randomized, double-blind, placebo-controlled design will allow an objective assessment of the efficacy and safety of LY3819253, alone and in combination with LY3832479, in preventing SARS-CoV-2 infection and COVID-19. A placebo-controlled design is appropriate because there are currently no therapeutic agents with proven benefit for prevention. The incidence of COVID-19 represents a clinically meaningful endpoint for a prevention study.

Residents and facility staff are included in this study as infected facility staff members may be important in the spread of SARS-CoV-2 within long term care facilities (Graham et al. 2020). Therefore, providing prophylactic treatment to both residents and facility staff may be highly beneficial in preventing or limiting COVID-19 outbreaks.

Studies have shown that following the identification of an index case, infection can spread rapidly among residents and facility staff in skilled nursing facilities (Arons et al. 2020; Graham et al. 2020). Therefore, randomization and treatment of participants within 7 days of identification of the first confirmed positive case of SARS-CoV-2 at a given facility is a requirement for study participation at that facility.

In Part 1, to facilitate rapid prophylaxis and treatment of residents and facility staff, participants will be enrolled prior to assessment of baseline SARS-CoV-2 RT-PCR or serology results, thus multiple analysis populations will exist. This includes separate prevention and treatment analysis populations and baseline serology positive participants. However, the primary analysis population for evaluation of efficacy in preventing SARS-CoV-2 and COVID-19 will be restricted to participants who are SARS-CoV-2 negative by RT-PCR and serology negative at baseline. Exploratory analyses will be conducted to evaluate efficacy of LY3819253 for treatment in participants who are SARS-CoV-2 positive by RT-PCR and serology negative at baseline.

Monoclonal antibodies may provide benefit for the treatment of mild to moderate COVID-19 (FDA EUA fact sheet 2020). Therefore, prior to randomization in Part 2, participants will receive a POC test for SARS-CoV-2 infection. Participants will be assigned to either Prevention or Treatment Cohorts based on the result of this POC test. Despite using a SARS-CoV-2 POC test during screening to assign participants to either the Prevention or Treatment cohorts, baseline SARS-CoV-2 RT-PCR and serology test results will be used to determine the study analysis populations. Refer to Section 9.3, Populations for Analyses, for further information on study analysis populations and treatment arms.

Part 3 of the study is a two-arm, outpatient, open-label, exploratory cohort evaluating the efficacy and safety of LY3819253 and LY3819253 in combination with LY3832479 in participants positive for SARS-CoV-2 with or without symptoms in staff and residents who are at higher risk for more severe disease and hospitalization in skilled nursing and assisted living facilities. For Part 3 only, participants who were in independent living situations at the facilities could be enrolled to the study.

SARS-CoV-2 vaccines are now available to the public. Those who received a vaccine are now allowed in the study to assess the safety of LY3819253 and LY3832479 after a person received a SARS-CoV-2 vaccine.

4.3. Justification for Dose

Part 1

The 4200 mg single dose LY3819253 is selected for this study based on preliminary safety, tolerability, PK data from the first-in-human Study PYAA, and preclinical PK/PD modeling. Based on an estimated human half-life of approximately 19 days, a single dose of 4200 mg may be necessary to have a sustained lung concentration above the *in vitro* IC₉₀ of viral cell-entry neutralization in 100% of participants for 4 weeks and in 90% of participants for a minimum of 8 weeks.

Part 2 and Part 3

LY3819253

LY3819253 700 mg was estimated as the maximum therapeutic dose based on PK/PD viral dynamics modeling and observed data from Study PYAB and has a sustained concentration above the *in vitro* IC₉₀ of viral cell-entry neutralization in the lung tissue (95th percentile of the estimates used) for at least 28 days in 90% of the participant population. The lower dose of 350 mg was selected to evaluate the lower limit of the confidence interval for clinical IC₉₀, based on emerging data from ongoing study. At dose levels greater than 700 mg, LY3819253 provides exposure coverage in at least 90% of participant population for approximately 8 weeks.

LY3832479

The LY3832479 1400 mg dose was selected as the maximum therapeutic dose based on PK/PD viral dynamics modeling, relative IC₉₀ potency to LY3819253, and has a sustained concentration above the *in vitro* IC₉₀ of viral cell-entry neutralization in the lung tissue for at least 28 days in 90% of the participant population. The LY3832479 700 mg dose was selected to evaluate the lower limit of the confidence interval for clinical IC₉₀. On average, the 3 dose levels are expected to provide exposure coverage (as described in Part 1) for approximately 8 weeks. At dose levels greater than 700 mg, LY3832479 provides exposure coverage in at least 90% of participant population for at least 8 weeks.

LY3819253 + LY3832479 Combination

To provide coverage of the different but overlapping epitopes on SARS-CoV-2 receptor binding domain sites, the dose selection rationale for each single mAb intervention in the combination is the same as for the individual dose rationale for a single mAb intervention described above.

4.4. End of Study Definition

A participant is considered to have completed the study if they have completed all required phases of the study including the last scheduled assessment shown in the SoA.

The end of the study is defined as the date of last scheduled assessment shown in the SoA for the last participant in the trial.

5. Study Population

Prospective approval of protocol deviations to recruitment and enrollment criteria, also known as protocol waivers or exemptions, is not permitted.

Due to the criticality of participant health, verbal interview of the potential participant, their legal authorized representative, or family member, may be the source for pre-existing conditions and medical history, unless otherwise specified within the eligibility criteria.

5.1. Inclusion Criteria

Participants are eligible to be included in the study only if all of the following criteria apply:

1. Are ≥ 18 years of age at the time of randomization
2. For Part 1 and Part 2 participants: Resident or staff in a skilled nursing or assisted living facility with at least one confirmed case of SARS-CoV-2 detection ≤ 7 days prior to randomization.
3. Reproductive and Contraceptive agreements and guidance are provided in Section 10.4, Appendix 4. Contraceptive use by men or women should be consistent with local regulations for those participating in clinical studies.
4. Agree to the collection of nasal, mid-turbinate, oropharyngeal, and nasopharyngeal swabs, and venous blood as specified in the schedule of activities.
5. Have venous access sufficient to allow intravenous infusions and blood sampling as per the protocol.
6. The participant or legally authorized representative gives signed informed consent as described in Section 10.1.3, Appendix 1, which includes compliance with the requirements and restrictions listed in the informed consent form (ICF) and in this protocol.

Part 3 participants only:

19. Resident or staff in a skilled nursing or assisted living facility who satisfies at least one of the following at the time of screening
 - Are ≥ 65 years of age
 - Have a BMI ≥ 35
 - Have chronic kidney disease
 - Have type 1 or type 2 diabetes
 - Have immunosuppressive disease
 - Are currently receiving immunosuppressive treatment, or
 - Are ≥ 55 years of age AND have
 - cardiovascular disease, OR
 - hypertension, OR
 - chronic obstructive pulmonary disease or other chronic respiratory disease

Note: BMI is rounded to the nearest whole number, for example, 34.5 is rounded to 35.

20. Positive SARS-CoV-2 test and infusion within 10 days of symptom onset, OR positive SARS-CoV-2 test and infusion within 10 days of testing if asymptomatic

5.2. Exclusion Criteria

Participants are excluded from the study if any of the following criteria apply:

7. For Parts 1 and 2, recovered from COVID-19 disease or asymptomatic infection
8. For Parts 1 and 2, a prior history of a positive SARS-CoV-2 serology test
9. For Parts 1 and 2, a history of Convalescent COVID-19 plasma treatment
10. Are an inpatient in hospital
11. For Parts 1 and 2, participation in a previous SARS-CoV-2 vaccine trial or received an approved SARS-CoV-2 vaccine
12. For Parts 1 and 2, previous receipt of SAR-CoV-2-specific monoclonal antibodies
13. Have participated, within the last 30 days, in a clinical study involving an investigational product. If the previous investigational product has a long half-life, 5 half-lives or 30 days (whichever is longer) should have passed. This criterion does not apply to products described in Criteria 9, 11, and 12.
14. Are pregnant or breast feeding
15. Are concurrently enrolled in any other type of medical research judged not to be scientifically or medically compatible with this study
16. Have known allergies to related compounds of LY3819253, LY3832479 or any components of the formulation
17. Suspected or proven serious, active bacterial, fungal, viral, or other infection that in the opinion of the investigator could constitute a risk when taking investigational product
18. Have any serious concomitant systemic disease, condition or disorder that, in the opinion of the investigator, should preclude participation in this study.

5.3. Lifestyle Considerations

Reproductive and Contraceptive guidance is provided in Section 10.4, Appendix 4.

Participants should refrain from donating blood or blood products from the time of their screening visit until 90 days following the last dose of study intervention.

5.4. Screen Failures

Screen failures are defined as participants who consent to participate in the clinical study but are not subsequently enrolled in the study. A minimal set of screen failure information is required to ensure transparent reporting of screen failure participants to meet the Consolidated Standards of Reporting Trials publishing requirements and to respond to queries from regulatory authorities. Minimal information includes demography, screen failure details, eligibility criteria, and any serious adverse event (SAE).

Individuals who do not meet the criteria for participation in this study (screen failure) may not be rescreened. Re-evaluation of venous access does not constitute rescreening and is allowable within the screening window.

6. Study Intervention

Study intervention is defined as any investigational intervention(s), marketed product(s), placebo, or medical device(s) intended to be administered to a study participant according to the study protocol.

6.1. Study Intervention(s) Administered

Each participant will receive a single IV infusion of either placebo, LY3819253, or a combination of LY3819253 and LY3832479.

Study Part	1 & 2	1	2 & 3	2 (Prevention Only)	2 & 3 (Treatment only)
Intervention Name	Placebo	LY3819253	LY3819253	LY3819253 + LY3832479	LY3819253 + LY3832479
Dose Formulation	0.9% sodium chloride solution			Solution	
Dosage Level(s)	Not applicable	4200 mg	700 mg	350 mg + 700 mg	700 mg + 1400 mg
Use	Placebo			Experimental	
IMP and NIMP	IMP			IMP	
Sourcing	Commercially available 0.9% sodium chloride solution			From Lilly	
Packaging and Labeling	Commercially available 0.9% sodium chloride solution			Study Intervention will be provided in glass vials and will be labeled appropriately	

Abbreviations: IMP = investigational medicinal product; IV = intravenous; NIMP = non-investigational medicinal product.

The infusion rate may be reduced as deemed necessary if an infusion reaction is observed (Section 6.1.1.2). Participants will be monitored for signs and symptoms of infusion reaction

- every 30 minutes during the infusion or at least once if infusion time is <30 minutes, and
- for at least 1 hour after completion of the infusion.

The site must have resuscitation equipment, emergency drugs, and appropriately trained site staff available during the infusion and for at least 1 hour after the completion of the infusion.

Infusion information may be found in the Dosing Solution Preparation Instructions.

6.1.1. Special Treatment Considerations

6.1.1.1. Premedication for Infusions

Premedication for infusions is not planned. However, if the participant has a medical history suggesting a potential benefit from premedication, the study investigator(s) or qualified designee should determine the appropriate premedication.

The investigators and sponsor may decide to use premedication if the frequency of infusion reactions among participants warrants it.

If minor infusion reactions are observed, administration of acetaminophen, 500-mg to 1000-mg, antihistamines and/or other appropriately indicated medications may be given prior to the start of infusions for subsequent participants.

The decision to implement premedication for infusions in subsequent participants will be made by the investigator and sponsor and recorded in the study documentation.

Any premedications given will be documented as a concomitant therapy.

6.1.1.2. Management of Infusion Reactions

All participants should be monitored closely, as there is a risk of infusion reaction and hypersensitivity (including anaphylaxis) with any biological agent.

Symptoms and Signs

Symptoms and signs that may occur as part of an infusion reaction include, but are not limited to fever, chills, nausea, headache, bronchospasm, hypotension, angioedema, throat irritation, rash including urticaria, pruritus, myalgia, and dizziness.

Infusion-related reactions severity will be assessed and reported using the Division of AIDS (DAIDS) Table for Grading the Severity of Adult and Pediatric Adverse Events, Corrected Version 2.1 (July 2017).

This table describes the severity of reactions according to DAIDS.

Parameter	Mild	Moderate	Severe	Severe and Potentially Life-threatening
Acute Allergic Reaction	Localized urticaria (wheals) with no medical intervention indicated	Localized urticaria with intervention indicated OR Mild angioedema with no intervention indicated	Generalized Urticaria OR Angioedema with intervention indicated OR Symptoms of mild bronchospasm	Acute anaphylaxis OR Life-threatening bronchospasm OR Laryngeal edema
Cytokine Release Syndrome ^a	Mild signs and symptoms AND Therapy (that is, antibody infusion) interruption not indicated	Therapy (that is, antibody infusion) interruption indicated AND Responds promptly to symptomatic treatment OR	Prolonged severe signs and symptoms OR Recurrence of symptoms following initial improvement	Life-threatening consequences (for example, requiring pressor or ventilator support)

		Prophylactic medications indicated for ≤ 24 hours		
--	--	--	--	--

^a A disorder characterized by nausea, headache, tachycardia, hypotension, rash, and/or shortness of breath.

Source: DAIDS Table for Grading the Severity of Adult and Pediatric Adverse Events, Corrected Version 2.1 (July 2017).

Site Needs

The clinical site should have necessary equipment and medications for the management of any infusion reaction, which may include but is not limited to oxygen, IV fluids, epinephrine, acetaminophen and antihistamine.

Management of Infusion Reactions

Investigators should determine the severity of the infusion reaction and manage infusion reactions based on standard of care and their clinical judgment. If an infusion reaction occurs, then supportive care should be used in accordance with the signs and symptoms.

If a participant permanently discontinues from study intervention, they should complete AE monitoring and other procedures as stated in the SoA.

6.2. Preparation/Handling/Storage/Accountability

The investigator or designee must confirm appropriate temperature conditions have been maintained during transit for all study intervention received and any discrepancies are reported and resolved before use of the study intervention.

To protect blinding, the interventions must be prepared by an unblinded site staff qualified to prepare study intervention who are not involved in any other study-related procedures. Instructions for preparation will be provided by the sponsor.

Only participants enrolled in the study may receive study intervention and only site staff may supply or administer study intervention.

All study intervention must be stored in a secure, environmentally controlled, and monitored (manual or automated) area in accordance with the labeled storage conditions with access limited to the investigator and authorized site staff.

The investigator, institution, contracted pharmacist, or another appropriate individual who is under the supervision of the investigator is responsible for study intervention accountability, reconciliation, and record maintenance (i.e., receipt, reconciliation, and final disposition records).

Further guidance and information for the final disposition of unused study interventions are provided in the pharmacy manual.

6.3. Measures to Minimize Bias: Randomization and Blinding

Randomization

Participants who meet all criteria for enrollment will be randomized on Day 1 as follows:

- In Part 1, 1:1 to double-blind treatment
- In Part 2, will be allocated as follows:
 - Prevention Cohort: 1:1:1 to double blinded treatment
 - Treatment Cohort: 1:1, as described in Part 2 Treatment Cohort below
- In Part 3, 1:1 to open label treatment

To achieve between-group comparability, block randomization within each facility will be used. Randomized participants within the facility will be stratified by role within the facility (resident versus facility staff), by sex, and whether or not the participant received a SARS-CoV-2 vaccine prior to screening (in Part 3 only).

All participants will be centrally randomized to study intervention using an Interactive Web Response System (IWRS). Before the study is initiated, the log in information and directions for the IWRS will be provided to each site.

Blinding

Part 1 and Part 2 Prevention Cohort

Part 1 and Part 2 are blinded. Neither participants, nor investigators, nor the sponsor study team will be aware of treatment assignments prior to the final database locks at the conclusion of the study, except as described in the following note.

Note: It is possible that some participants will have the SARS-CoV-2 negative result on the screening point of care test, but could be positive on the baseline SARS-CoV-2 PCR test. The results from the baseline PCR test will not be available until after the participant is randomized. Once positive results are known from the baseline PCR test, these participants will be unblinded and have the option to continue to be followed for safety according to the Prevention Cohort SoA. This table describes general procedures for unblinding.

Unblinding (IWRS)	
 • Emergency unblinding for adverse events may be performed through the IWRS. All actions resulting in an unblinding event are recorded and reported by the IWRS • In case of an emergency, the investigator has the sole responsibility for determining if unblinding of a participant's intervention assignment is warranted • Participant safety must always be the first consideration in making such a determination. However, the investigator should make all attempts to contact the Medical Monitor in advance of unblinding • If a participant's intervention assignment is unblinded, the sponsor must be notified immediately after breaking the blind even if consultation occurred in advance • The date and reason that the blind was broken must be recorded in the source documentation. • Participants who test negative at screening POC testing, then test positive at baseline PCR testing, will be unblinded. Unblinding is recorded and reported by the IWRS.
-------------------	--

Abbreviations: IWRS = interactive web-response system.

If an investigator, site staff performing assessments, or participant is unblinded while the infusion is ongoing, the participant must be discontinued from the study intervention and the

infusion stopped. If any amount of study intervention was administered, follow procedures according to the SoA as described in Section 7.1.

Part 2 Treatment Cohort

The Part 2 Treatment Cohort is blinded. Neither participants, nor investigators, nor the sponsor study team will be aware of treatment assignments prior to the final database locks at the conclusion of the study.

If the participant is assigned to the Part 2 treatment cohort based on a positive POC test, the participant will be randomized to one of two arms. The participant will be informed that they are receiving active study intervention (that is, not placebo).

Part 3

Part 3 is open label.

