Part 3 objectives are exploratory and therefore described in [Section 3](#).

Overall Design

Study J2X-MC-PYAD is a randomized, double-blind, placebo-controlled, prophylaxis study to evaluate the efficacy and safety of intravenous LY3819253, alone and in combination with LY3832479, in preventing SARS-CoV-2 infection and COVID-19, compared to placebo. An independent Data Safety Monitor Board (DSMB) will actively monitor interim data to make recommendations about early study closure or changes to sample size.

Disclosure Statement: This is a three-part, 9-arm interventional study that is double-blinded.

Number of Participants:

For Part 1, a total of approximately 1700 participants (intent-to-treat [ITT] population) will be randomly assigned to study intervention such that approximately 1300 SARS-CoV-2 RT-PCR and serology negative participants are randomized in the study with the goal of achieving approximately 33 events (in each of the primary and key secondary endpoints) in the prevention population.

For Part 2, a total of approximately 2000 participants will be randomly assigned to study intervention based on rapid point of care (POC) testing such that approximately 1700 participants SARS-CoV-2 RT-PCR and serology negative participants are randomized in the Prevention Cohort with the goal of achieving approximately 56 events on each of the primary and key secondary endpoints.

Part 3 will enroll at least 30 participants and up to approximately 500 participants randomized to study intervention.

The maximum sample size for this study is approximately 5000 participants in the ITT population.

Intervention Groups and Duration:

Participants will receive one intravenous infusion of study intervention.

The maximum total duration of study participation for each participant of the prevention groups is 24 weeks.

The maximum total duration of study participation for each participant of the treatment group is 12 weeks.

Part 1:

Eligible participants will be randomized to one of two arms: placebo or LY3819253 4200 mg.

Participants will continue to enroll to Part 1 until the needed events for the primary and key secondary endpoints are achieved and the minimum number of residents enroll.

The evaluation period for Part 1 is 8 weeks, with follow-up to 24 weeks.

Part 2:

The Sponsor will decide when to trigger activation of Part 2. Activation of Part 2 will be communicated to sites.

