### 5.3.2. Blinding

Parts 1 and 2 of this study are double-blinded. Neither participants, nor investigators, nor the sponsor study team will be aware of treatment assignments prior to the final data base lock at the conclusion of the study.

Note: It is possible that some participants have SARS-CoV-2 negative result on the screening point of care test, but could be positive on the baseline SARS-CoV-2 PCR test. The results from the baseline test will not be available until after the participant is randomized. Once positive results are known from the baseline test, these participants will be unblinded and have the option to continue to be followed according to the Prevention Cohort SoA. Unblinded participants will not be included as part of the defined prevention population. [Table PYAD.5.1](#) describes general procedures for unblinding.

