### **6.1.5. Timing of Primary Analysis**

#### **6.1.5.1. Part 1 Primary Analysis**

To ensure that all primary and key secondary endpoints are well-powered, database lock for the primary and key secondary endpoints in Part 1 (the Part 1 Primary Database Lock) will be triggered when at least 300 facility residents have been enrolled and when 33 participants in the Part 1 Prevention population experience a moderate or worse severity case of COVID-19. All pre-specified analyses will be based on the Primary Database Lock. However, if the accumulation of moderate or worse severity cases of COVID-19 occurs slower than expected, the Primary Database Lock may be triggered when at least 36 participants in the Part 1 Prevention population test positive for SARS-CoV-2 within 4 weeks of randomization. If this is the case, only the primary endpoint will be evaluated at the Primary Database Lock. At the time of the primary analysis for Part 1, only data from patients enrolled in Part 1 will be unblinded to the sponsor.

To account for participants who have not finished the Evaluation Period at the time of the Primary Database Lock, a supplementary database lock (the Part 1 End of Evaluation Database Lock) will occur once all participants have completed the Evaluation Period or discontinued from the study. The analyses conducted during the Primary Database Lock will be re-evaluated at the End of Evaluation Database Lock.

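### Both blinding sections keep the sponsor study team blinded to the end of the study, but SAP 6.1.5.1 unblinds Part 1 to the sponsor at an event-triggered lock, with no stated limit on who sees assignments

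*Protocol*

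**What the plan says.** **Blinding rule.** Protocol 6.3 covers Part 1 and the Part 2 Prevention Cohort. After naming participants and investigators it continues: "nor the sponsor study team will be aware of treatment assignments prior to the final database locks at the conclusion of the study". The exceptions it gives are Part 2 participants who are negative on the screening point-of-care test but positive on the baseline PCR, and emergency unblinding. SAP 5.3.2 has the same rule with a single lock: "nor the sponsor study team will be aware of treatment assignments prior to the final data base lock at the conclusion of the study".

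**Part 1 primary analysis.** SAP 6.1.5.1 triggers the Primary Database Lock when at least 300 residents have enrolled and "33 participants in the Part 1 Prevention population experience a moderate or worse severity case of COVID-19". If such cases come slowly, the trigger may instead be at least 36 infections within 4 weeks of randomization, and only the primary endpoint is then evaluated at that lock. The section adds: "At the time of the primary analysis for Part 1, only data from patients enrolled in Part 1 will be unblinded to the sponsor".

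**What follows the lock.** A supplementary lock is planned: "To account for participants who have not finished the Evaluation Period at the time of the Primary Database Lock". Then: "The analyses conducted during the Primary Database Lock will be re-evaluated at the End of Evaluation Database Lock". On enrolment and duration, the Protocol synopsis says: "Participants will continue to enroll to Part 1 until the needed events for the primary and key secondary endpoints are achieved" (with a resident minimum as well), and "The evaluation period for Part 1 is 8 weeks, with follow-up to 24 weeks".

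**Part 2.** SAP 6.1.5.2 has the same two-lock structure but says nothing about who is unblinded at the first lock.

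**The concern.** The two blinding sections make a promise that the analysis-timing section does not keep. A sponsor team that knows each Part 1 assignment would be in place while Part 1 data are still arriving, and those data feed later analyses.

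The route for bias is on the sponsor side. The sponsor is responsible for data management and quality checking (Protocol 10.1.7). Severity comes from Table 1 of the Protocol, whose lists of symptoms and signs are given as examples, and which names shock without criteria. Queries, cleaning decisions and any severity derivation made after unblinding could be influenced by knowledge of the arm. Even if none were, the later analyses could not be reported as double-blind in the sense of the Protocol's own abbreviations appendix, which includes sponsor staff involved in treatment or clinical evaluation.

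**Working it through.** **1. The trigger.** Inputs from Protocol 9.2 and 6.3: two-sided alpha 0.05, power 90%, risk ratio 0.33, 1:1 allocation, Schoenfeld's formula.

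Events = (1.960 + 1.282)² / (0.25 × (ln 0.33)²) = 34.2, or 35 rounded up. With the hazard ratio implied by 4.0% versus 1.32%, ln(1 − 0.0132)/ln(1 − 0.04) = 0.3255, it is 34. Power at 33 events is 89.0%. The stated 33 is reproduced to within rounding and choice of input.

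**2. Where the lock falls.** With 650 per arm, expected events are 650 × 0.04 + 650 × 0.0132 = 26.0 + 8.6 = 34.6. The 33rd event therefore comes close to full planned accrual. But 34.6 assumes that all 1300 have complete 8-week follow-up. Either enrolment runs past 1300, or the lock trails the last enrolment. The documents do not settle which, so the lag is left free in step 5.

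**3. Is the Primary lock the end of the study?** Protocol 4.4 ends the study at the last scheduled assessment of the last participant. Part 1 follow-up runs to Day 169. A lock at which some participants have not finished Day 57 is not the conclusion of the study, whether the blinding rule means one final lock or several.

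**4. Which analyses use data collected after unblinding?**
- The End of Evaluation repeat of the primary-lock analyses (SAP 6.1.5.1). At the Primary lock, anyone with at least one post-baseline PCR result and no event so far counts as event-free (SAP 6.3.1 and 6.3.2). The later lock is the first with the complete 8-week window.
- COVID-19 hospitalization or death, COVID-19 death and all-cause death at any time after randomization, all analysed at the End of Evaluation lock (SAP 6.10.3.4, 6.10.3.6, 6.16.2.6).
- Safety follow-up to Day 169.
- On the fallback route, both key secondary endpoints. They belong to the multiplicity-controlled scheme of SAP 6.5 but are not evaluated at the Primary lock, so they would be tested after the sponsor is unblinded.

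**5. How many participants?** No accrual time is given, so this is illustrative. Assume uniform accrual over T weeks, and L weeks from last enrolment to unblinding. The share still in the 8-week evaluation is (8 − L)/T when T is at least 8, and zero when L is 8 or more.

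| T (weeks) | L = 0 | L = 4 | L ≥ 8 |
|---|---|---|---|
| 12 | 67% | 33% | 0 |
| 16 | 50% | 25% | 0 |
| 24 | 33% | 17% | 0 |

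Of 1300, the zero-lag column is about 867, 650 and 433. Real accrual would be less even, since each facility enrols within 7 days of an index case.

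For the 24-week follow-up the share is (24 − L)/T, capped at 1. At L = 8 it is 100% for T = 12 and T = 16, and 16/24 = 67% for T = 24. A long lag removes the exposure of the 8-week window but not that of the safety follow-up.

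**The case against.** The strongest defence is that an event-driven primary analysis is legitimate and this one is protected. The SAP bases all pre-specified analyses on the Primary lock and calls the End of Evaluation lock supplementary. Incomplete follow-up is addressed by weighted supplementary analyses (SAP 6.3.1, 6.3.2) and by censoring in the Cox model (SAP 6.10.2.2). This stands for the primary endpoint. It does not cover the key secondary endpoints on the fallback route, or the analyses first planned for the later lock.

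Second, the sponsor judges few outcomes. PCR is read centrally, COVID-19 death is according to the investigator, and vital signs and symptoms entered directly into the electronic data capture system are the source record. This also stands, and it narrows the mechanism to cleaning, querying and severity derivation.

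Third, the texts might be reconciled. The plural in Protocol 6.3 could mean one lock per part, but the words on the conclusion of the study do not fit that reading. The SAP says the sponsor, while the Protocol says the sponsor study team, so a small separate unblinded group is possible. Protocol 9.5 and SAP 6.15.2 refer to a separate unblinding plan, which may define such a group. Neither document describes one for this lock, and an unseen plan does not remove the conflict in these texts.

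Fourth, Table 1 is pre-specified and SAP Version 3 was approved before unblinding. That helps, but open-ended criteria leave room in the derivation unless it too is frozen.

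**Conclusion.** The conflict is in the current text of both documents and is more than wording, because data collected after the unblinding feed planned analyses, including confirmatory ones if the fallback is used. Up to 67%, 50% or 33% of Part 1 could be inside the 8-week window for 12, 16 or 24 weeks of accrual. These are zero-lag upper bounds under an assumed uniform accrual; the true share could be nil.

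A reader might infer four stronger things that the documents do not support:
- **The Part 1 primary test is biased or its type I error inflated.** Its data are locked before the sponsor is unblinded.
- **The sponsor classifies COVID-19 relatedness knowing the arm.** No section gives the sponsor that task.
- **Sites or participants are unblinded at this lock.** The SAP mentions only the sponsor.
- **Enrolment continues past the lock.** The Protocol makes reaching the needed events and the resident minimum the planned end of Part 1 enrolment.

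Nor does SAP 6.1.5.2 unblind the sponsor at the Part 2 Primary lock; it is silent.

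**What to change.** Reword SAP 6.1.5.1 so that, at the Part 1 Primary Database Lock:
- participant-level assignments go only to the analysts named in the separate unblinding plan;
- sponsor staff who clean, query or derive ongoing Part 1 data stay blinded until the Part 1 End of Evaluation lock;
- sites and participants stay blinded until their last visit;
- the severity derivation is frozen before the lock.

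Name these locks in Protocol 6.3 and SAP 5.3.2 in place of the single end-of-study statement, and state the same rule for the Part 2 Primary lock in SAP 6.1.5.2.

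The cost is wording in the SAP and the unblinding plan, a small Protocol text change (with ethics committee approval if it is made as an amendment), and up to about 8 weeks in which the wider sponsor team sees only group-level Part 1 results. The primary analysis is not delayed, and no alpha, event count or sample size changes. Sponsor handling of follow-up after the End of Evaluation lock would still be unblinded; the fix accepts this openly and relies on blinded sites and participants for that period.
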